## 5.2. Exclusion Criteria

Participants are excluded from the study if **any** of the following criteria apply:

### Medical Conditions

15. For patients who have received prior immunotherapy, the following patients will be excluded:
- Experienced a Grade 4 immune-related toxicity or any immune-related toxicity that led to permanent discontinuation of prior anti-PD-1, anti-PD-L1, or other immunotherapy
  - Experienced a less than or equal to Grade 3 irAE that has not recovered to Grade 1 after use of high dose corticosteroids that occurred during prior immunotherapy [exceptions: endocrine disorders where patients with prior endocrine AEs are permitted to enroll if they are asymptomatic, considered clinically stable, and maintained on appropriate replacement therapy]
  - Any grade:
    - ocular irAE,
    - serious neurologic irAE (e.g., Guillain-Barre syndrome, myasthenia gravis, encephalitis)
    - Serious cardiovascular irAE (e.g., myocarditis)
  - Required immunosuppressive agents other than corticosteroids for the management of irAE; or currently requires maintenance doses of  $\geq 10$  mg prednisone/prednisolone (or equivalent) per day for irAE
16. Have interstitial lung disease or (noninfectious) pneumonitis; patients with a history of (noninfectious) pneumonitis Grade 2 or greater that required steroids ( $>7$  days) to assist with management
17. Have a serious concomitant systemic disorder that, in the opinion of the investigator, would compromise the patient's ability to adhere to the protocol
18. Human Immunodeficiency Virus (HIV) positive patients (HIV 1 and/or 2; screening not required) are excluded **unless** they are well controlled on highly active antiretroviral therapy with
- No evidence of acquired immunodeficiency syndrome (AIDS)-defining opportunistic infections within the last 2 years, and
  - CD4 count  $>350$  cells/ $\mu$ l

- HIV infected participants with a history of Kaposi's sarcoma and/or Multicentric Castleman's Disease are not eligible.

19. Have active hepatitis B or C virus infection (screening required)
20. Have current untreated tuberculosis
21. Have active infection requiring systemic therapy
22. Have prior or second concurrent primary malignancies that, in the judgment of the investigator and the Lilly CRP/CRS, may affect the interpretation of results. Patients with carcinoma in situ of any origin and patients with prior malignancies who are in remission and whose likelihood of recurrence is very low (such as basal cell carcinoma), as judged by the Lilly CRP/CRS, are eligible for this study
23. Have active or suspected autoimmune disease (e.g., autoimmune vasculitis, autoimmune myocarditis) or any illness or treatment that could compromise the immune system (e.g., prior solid organ transplant) within the past 2 years, or a syndrome or condition that requires continuous systemic corticosteroids or immunosuppressive agents.

This criterion does not apply to patients with: (i) vitiligo, alopecia, or type I diabetes mellitus; (ii) residual hypothyroidism due to an autoimmune condition requiring only hormone replacement; or (iii) psoriasis not requiring chronic systemic immunosuppressive treatment within the past 2 years, not expected to recur in the absence of an external trigger, (iv) autoimmune-mediated hypothyroidism that is stable on hormone replacement; (v) Raynaud's syndrome; or (vi) Sjogren's syndrome. Patients with resolved childhood asthma/atopy are allowed.

24. Are at risk of vascular inflammation, such as those with a history of angiitis, arteritis, or hypersensitivity vasculitis as an adverse reaction to medication, for example, are not eligible.
25. Are being treated with escalating or chronic supraphysiologic doses of corticosteroids or immunosuppressive agents (such as, exceeding 10 mg/day of prednisone or equivalent). Use of topical, ophthalmic, inhaled, intermittent steroid injections, and intranasal corticosteroids permitted.
26. Patients with conditions that may impact absorption of LY3475070, such as bowel obstruction, uncontrolled diarrhea, or extensive intestinal resection.
27. Have moderate or severe cardiovascular disease, such as the following:
  - a) presence of cardiac disease, including a myocardial infarction or any other arterial thrombotic event, blood clots not limited to deep vein thrombosis, cerebrovascular accident or transient ischemic attack within 6 months prior to enrollment; unstable angina pectoris; New York Heart Association Class III/IV congestive heart failure; aneurysm of major vessels or heart; left ventricular ejection fraction <50% (evaluation based on institutional lower limit of normal); or uncontrolled hypertension

- b) severe, moderate, or clinically significant valvulopathy; documented major ECG abnormalities that, in the judgment of the investigator, are clinically significant (for example, symptomatic arrhythmias or arrhythmias requiring treatment; myocardial infarction within the last 3 months; or mean corrected QT interval (QTc) >450 msec for male participants or QTc >470 msec for female participants or QTc >480 msec in participants with bundle branch block calculated using Fredericia's correction and confirmed by triplicate ECG.
  - c) previous cardiotoxic cancer treatment associated with type 1 damage such as anthracyclines (e.g., daunorubicin, doxorubicin, epirubicin, idarubicin) and previous thoracic radiotherapy with a field involving the heart.
28. Have symptomatic central nervous system (CNS) malignancy or metastasis and/or carcinomatous meningitis (screening not required). Patients with treated CNS metastases are eligible for this study if they are not currently receiving corticosteroids (exceeding 10 mg/day prednisone or equivalent) and/or anticonvulsants to treat CNS metastases, and their disease is asymptomatic and radiographically stable for at least 30 days.
29. Have received a live vaccine within 30 days before the first dose of study treatment. Examples of live vaccines include, but are not limited to, the following: measles, mumps, rubella, chicken pox, yellow fever, rabies, Bacillus Calmette–Guérin, and typhoid vaccine. Seasonal influenza vaccines for injection are generally killed virus vaccines and are allowed; however, intranasal influenza vaccines are live attenuated vaccines and are not allowed.
30. Post-partum patient who is or plans to breast-feed during the study
31. Has a known psychiatric or substance abuse disorder that would interfere with the participant's ability to cooperate with the requirements of the study
32. Have current or history of allergy or hypersensitivity to LY3475070 components including allergy to beta lactam antibiotics.
33. Has severe hypersensitivity to pembrolizumab and/or any of its excipients.
34. Has had an allogenic tissue/solid organ transplant.

#### **Prior Therapy**

35. Has received prior purinergic based inhibitors defined as adenosine A2AR, A2BR, A3, CD39 or CD73.
36. Has undergone prior allogeneic hematopoietic stem cell transplantation within the last 5 years. Patients who have had a transplant greater than 5 years ago are eligible as long as they have no symptoms of graft versus host disease.

#### **Prior/Concurrent Clinical Study Experience**

37. Patient is currently enrolled in any other clinical study involving an investigational product or any other type of medical research judged not to be scientifically or medically compatible with this study by the investigator and Lilly CRP/CRS.

### **5.3. Lifestyle Considerations**

Not applicable.

### **5.4. Screen Failures**

Individuals who do not meet the criteria for participation in this study (screen failure) may be rescreened. Rescreened participants should be assigned a new participant identification number. The interval between rescreening should be  $\geq 2$  weeks. Each time rescreening is performed, the individual must sign a new ICF and will be assigned a new identification number. A patient may not be rescreened in an effort to obtain a different CD73 result. Repeating of laboratory tests during the screening period or repeating screening tests to comply with the protocol designated screening period does not constitute rescreening. This includes 1 repeat for CD73 expression to determine Phase 1b Cohort C eligibility if CD73 expression was not able to be determined by the patient's initial sample.

## 6. Study Intervention

Study intervention is defined as any investigational intervention(s), marketed product(s), placebo, or medical device(s) intended to be administered to a study participant according to the study protocol.

### 6.1. Study Intervention(s) Administered

Cohort	Dose Level	Oral LY3475070	IV Pembrolizumab
Cohort A	DL1	150mg QD	N/A
	DL2	300mg QD	N/A
	DL3	600mg QD	N/A
	DL4	1000mg QD	N/A
Cohort B	CDL1	150mg QD	200 mg Q3W
	CDL2	300mg QD	200 mg Q3W
	CDL3	600mg QD	200mg Q3W
Cohorts C1, D1 and E	RP1D c	RP1D/MTD	200 mg Q3W
Cohorts C2 and D2	RP1D m	RP1D/MTD	N/A

Abbreviations: CDL = combination dose level; DL = dose level; IV = intravenous; N/A = not applicable; MTD = maximum tolerated dose; RP1D = recommended phase 1 dose; RP1Dc = recommended phase 1 dose (for combination therapy); RP1Dm = recommended phase 1 dose (for monotherapy); Q3W = every 3 weeks; QD = once a day.

Note: Pembrolizumab should be administered for a maximum duration of 24 months (35 cycles).

A delay of a treatment day up to 7 days due to holidays, weekends, bad weather, unrelated medical events, or other unforeseen circumstances will be permitted and not be counted as a protocol deviation. The reason for interruption should be documented on the electronic case report form (eCRF).

The doses of LY3475070 will be administered at approximately the same times on each day, generally at home. Patients should be instructed take LY3475070 on an empty stomach, if possible. Otherwise, drug capsules may be taken a minimum of 1 hour before eating or 2 hours after consumption of food. A LY3475070 administration patient diary must be kept for dosing compliance monitoring. The actual time of dose administrations will be transcribed and provided to the sponsor.

If BID dosing is evaluated, patients will take doses 12±2 hours apart (i.e., 10 to 14 hours between doses). There should at least be 10 hours between each subsequent dose.

At clinic visits, patients will be directed to take LY3475070 at the site. LY3475070 will be administered 30 to 60 minutes post administration of pembrolizumab.

Pembrolizumab will be administered using IV infusion on Day 1 of each 3-week treatment cycle after all procedures and assessments have been completed. Pembrolizumab will be administered as a dose of 200 mg using a 30-minute IV infusion. Sites should make every effort to target infusion timing to be as close to 30 minutes as possible. However, given the variability of

infusion pumps from site to site, a window between 5 minutes prior to and 10 minutes after administration is permitted (i.e., infusion time is 30 minutes (-5 min/+10 min).

The actual time of dose administrations will be transcribed and provided to the sponsor.

If LY3475070 is discontinued, pembrolizumab may be continued alone for up to 2 years (35 cycles). Conversely, if pembrolizumab is discontinued, LY3475070 may be continued alone.

### 6.1.1. Definition of DLT and DLT-ET

#### 6.1.1.1. DLT

A DLT is defined as any of the events listed in the table below, if both of the following criteria are met:

- the event occurs during the DLT observation period (28 days) in Phase 1a, and
- the event cannot, in the opinion of the investigator, be definitely attributed to primary disease or extraneous causes, such as accident.

Patients who experience a DLT in the DLT observation period will be discontinued from study treatment.

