#### Dose-Limiting Toxicities

Hematologic Toxicity
• Grade 3 thrombocytopenia associated with clinically significant bleeding and requiring platelet transfusion or Grade 4 thrombocytopenia of any duration
• Grade $\geq 3$ febrile neutropenia
• Grade $\geq 3$ anemia requiring a blood transfusion
• Other Grade $\geq 4$ toxicity, excluding toxicities listed below this table
Nonhematologic Toxicity – Nonlaboratory
• Grade $\geq 3$ irAE
• Grade $\geq 3$ colitis or noninfectious pneumonitis
• Grade $\geq 3$ pneumonitis or Grade 2 pneumonitis that does not show clinical improvement within 3 days after initiation of optimal medical management including corticosteroids therapy, which is then treated as Grade 3
• Grade $\geq 3$ nausea, vomiting or diarrhea that lasts more than 48 hrs despite optimal supportive care
• Grade $\geq 3$ fatigue lasting $>7$ days
• Grade $\geq 3$ hypertension despite maximal medical therapy
• Grade $\geq 3$ tachycardia
• Any other Grade $\geq 3$ toxicity
• Immune-related adverse event that necessitated permanent discontinuation of study drug(s), regardless of grade
Nonhematologic Toxicity – Laboratory/Investigations
• Any Grade $\geq 3$ laboratory abnormality except for specific exceptions listed below
• ALT or AST: 
 
○ <math>>8 \times</math> ULN
 
○ <math>\geq 2</math>-fold above the patient's baseline value that lasts <math>>7</math> days,
 
○ <math>\geq 3 \times</math> ULN with concomitant bilirubin <math>>2 \times</math> ULN, in the absence of cholestasis
 
○ Total bilirubin <math>>3 \times</math> ULN
 
○ <math>\geq</math>Grade 3 amylase or lipase that is associated with symptoms or clinical manifestations of pancreatitis
 

Please refer to Section 8.2.1.1 for additional hepatic safety monitoring guidance.

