**The following adverse events are not considered DLTs:**

- Toxicity that is clearly and directly related to the primary disease or to another etiology
- Grade 3 endocrine disorder (thyroid, pituitary, and/or adrenal insufficiency), if both the following criteria are met:
  - the disorder is manageable with or without systemic corticosteroid therapy and/or hormone replacement therapy, and
  - the patient is asymptomatic
- Grade 3 inflammatory reaction attributed to a local antitumor response (such as, inflammatory reaction in the lymph nodes or at sites of metastatic disease)
- Any grade vitiligo or alopecia
- $\geq$ Grade 3 electrolyte abnormality that lasts <72 hours, is not clinically complicated and resolves spontaneous or responds to conventional medical interventions
- $\geq$ Grade 3 amylase or lipase that is not associated with symptoms or clinical manifestations of pancreatitis
- Grade 3 or 4 neutropenia, provided **both** of the following criteria are met:
  - is not associated with fever or systemic infection, and
  - improves by at least 1 grade within 5 days
- Grade 3 or 4 lymphopenia

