## 6.6. Dose Modification

### 6.6.1. Dose Modification and Toxicity Management of LY3475070 for Non-immune-mediated AEs Associated with LY3475070 and/or in Combination with Pembrolizumab

Patient may receive up to 2 dose reductions for AEs attributed to LY3475070. LY3475070 treatment may be interrupted, dose reduced or discontinued due to toxicity per the tables below.

Patients who have dose delays of more than 14 days, unless a different duration is specified in the above table, should permanently discontinue from the study.

Due to its MOA, LY3475070 may induce irAEs that could affect any organ of the body. Previous trials with agents inhibiting the adenosine pathway have not reported irAEs to the same incidence rate as seen with other check point inhibitors such as CTLA4 or PD-1/L1. From the ongoing A2AR antagonist single agent data only rash/pruritus, and elevated LFTs have been reported. In the event other irAEs occur please consult the table provided in Section 6.6.1.2 for management of irAEs.

Related AEs	Toxicity Grade or Conditions (CTCAE v5.0)	Action Taken to Therapy	AE Management	Monitor and Follow-up
Non hematologic				
Acneiform Rash	Grade 1	Continue treatment	Initiate topical prophylactic antibiotic (e.g., clindamycin). Consider using low potency topical steroids (e.g., hydrocortisone 2.5%)	Monitor for worsening signs and symptoms.
	Grade 2	Withhold therapy until $\leq$ Grade 1 (for recurrent Grade 2, or toxicity lasting more than 2 weeks proceed as Grade 3). If immune mediated rash is suspected see below table for management of immune mediated AE's).	Initiate oral antibiotic (e.g., doxycycline). Initiate low potency topical steroid, if not already started. Consider skin biopsy if immune mediated toxicity is suspected	Monitor for worsening signs and symptoms weekly

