	Grade 3	Withhold therapy until $\leq$ grade 1 then dose reduce LY3475070 (if rash worsens or does not improve in two weeks permanently discontinue) If Stevens–Johnson syndrome or toxic epidermal necrosis permanently discontinue patient	Initiate oral antibiotic (e.g., doxycycline). Initiate systemic corticosteroid (e.g., prednisone 0.5 mg/kg daily (maximum dose, 40 mg). Consider dermatology consultation.	Monitor for worsening signs and symptoms weekly until improvement to $\leq$ Grade 1. Resume LY treatment with 1 DL reduction. If rash does not improve or worsens after 2 weeks of treatment, discontinue LY permanently. If Stevens–Johnson syndrome or toxic epidermal necrolysis is suspected, discontinue permanently.
	Grade 4	Permanently discontinue	Initiate oral antibiotic (e.g., doxycycline). Initiate systemic corticosteroid (e.g., prednisone 0.5 mg/kg daily (maximum dose, 40 mg). Consider dermatology consultation.	
Diarrhea	Grade 1	Continue LY3475070 treatment. Start loperamide 4 mg initially, followed by 2 mg every 4 hours or after each stool.	Consider discontinue of lactose containing products	

Related AEs	Toxicity Grade or Conditions (CTCAE v5.0)	Action Taken to Therapy	AE Management	Monitor and Follow-up
	Grade 2	Continue LY3475070 treatment if Grade 2 diarrhea lasts <48 hours. Hold LY3475070 treatment if Grade 2 diarrhea lasts ≥48 hrs treatment until resolution to ≤ Grade 1.	Start loperamide 4 mg initially, followed by 2 mg every 4 hours or after each stool. Encourage oral hydration. If immune mediated colitis is suspected, consider GI consultation and biopsy.	
	Grade 3	Hold LY3475070 until resolution to Grade ≤ 1. Resume LY at 1 DL lower upon recovery.	If not already done, start loperamide 4 mg initially, followed by 2 mg every 4 hours or after each stool. Consider hospitalization for symptom and fluid management and GI consultation.	
	Grade 4	Permanently discontinue LY3475070 treatment	Consider hospitalization for symptom and fluid management, hydration and GI consultation.	
AST/ALT elevation or Increased bilirubin	Grade 1	Continue LY3475070 treatment	Review concomitant medications and alcohol use	

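### Protocol 6.1.1.1 ends study treatment after a Phase 1a DLT, but several rows of the 6.6.1 table and the hypothyroidism row of 6.6.2 direct reduced, resumed or continued dosing for events that are DLTs

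*Protocol*

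**What the plan says.** Protocol 6.1.1.1 defines a DLT as a listed event that occurs in the 28-day Phase 1a observation period and cannot be definitely attributed to the disease or to extraneous causes. It then states: "Patients who experience a DLT in the DLT observation period will be discontinued from study treatment". No exception follows.

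Section 6.6.1 covers LY3475070 alone and with pembrolizumab, and allows up to two dose reductions. It introduces its table with "LY3475070 treatment may be interrupted, dose reduced or discontinued due to toxicity per the tables below". Neither the introduction nor the rows mention DLTs, the observation period or the study phase. Typical Grade 3 entries are "Resume LY treatment with 1 DL reduction" (acneiform rash) and "Resume LY at 1 DL lower upon recovery" (diarrhea).

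Section 6.6.2 gives actions for immune-related events, and its action column covers both drugs. Hypothyroidism of Grade 2, 3 or 4 is marked *Continue*. A Grade 3 or higher immune-related event is a DLT, and the relevant exemption reaches only a "Grade 3 endocrine disorder (thyroid, pituitary, and/or adrenal insufficiency), if both the following criteria are met", namely that it is manageable and the patient is asymptomatic.

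Section 7.1 lists the reasons for which treatment must stop. It names unacceptable toxicity and recurrent Grade 2 pneumonitis, but not a DLT.

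**The concern.** This is a first-in-human study, and two current sections give opposite dosing instructions for the same event in the same patient. A site managing toxicity will look at the toxicity tables, which never point back to 6.1.1.1. If it follows them, it may re-dose, or never stop, a patient whom 6.1.1.1 takes off treatment. If it follows 6.1.1.1, it departs from the table. Section 8 does not allow waivers, so neither choice is clean on paper.

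**Working it through.** There is no plan figure to reproduce. The check sets each DLT criterion in 6.1.1.1 beside the action for the same event and grade in 6.6. The 6.6.1 table is for related events, so its events ordinarily meet the attribution condition for a DLT as well.

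**Section 6.6.1**

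| Event | DLT under 6.1.1.1 | Action in 6.6.1 |
|---|---|---|
| Fatigue | Grade 3 or higher for more than 7 days | Grade 3 beyond 7 days: reduce one level |
| Febrile neutropenia | Grade 3 or higher | Reduce one level on recovery to Grade 1 or below |
| Acneiform rash, Grade 3 | Caught by the entry for any other Grade 3 or higher toxicity | "Resume LY treatment with 1 DL reduction" |
| Other non-hematologic, Grade 3 | Same entry | Withhold, then reduce one level |
| Anemia, Grade 3 | Grade 3 or higher "anemia requiring a blood transfusion" | Resume one level lower; transfusion is listed as management |
| Thrombocytopenia, Grade 3 | "Grade 3 thrombocytopenia associated with clinically significant bleeding and requiring platelet transfusion" | With bleeding, resume one level lower; platelet transfusion is listed as management |
| Diarrhea, Grade 3 | Grade 3 or higher "nausea, vomiting or diarrhea that lasts more than 48 hrs despite optimal supportive care" | "Resume LY at 1 DL lower upon recovery" |
| ALT/AST or bilirubin, Grade 3 | ALT/AST above 8× ULN, or bilirubin above 3× ULN | Resume one level lower if no hepatocellular injury |

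The first two rows use the same trigger in both places, with opposite actions. The anemia, thrombocytopenia, diarrhea and hepatic rows collide only when the DLT qualifier is met.

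**Hepatic overlap.** Section 6.6.1 prints no numerical limits for Grade 3. I take those in footnote b of the 6.6.2 table (normal baseline), assuming that they describe Grade 3 in both tables, since both cite CTCAE v5.0.
- Bilirubin: Grade 3 is >3 to 10× ULN and the DLT limit is >3× ULN, so all of Grade 3 is inside it.
- ALT/AST: Grade 3 is >5 to 20× ULN and the DLT limit is >8× ULN, so the overlap is >8 to 20× ULN.
- Section 6.6.1 describes hepatocellular injury as transaminase ≥3× ULN with total bilirubin ≥2× ULN, and stops treatment then. The conflict is therefore limited to cases such as ALT above 8× ULN with bilirubin below 2× ULN, or bilirubin above 3× ULN with transaminases below 3× ULN.

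**Section 6.6.2**
- *Direct conflict:* hypothyroidism. Grade 4, or symptomatic Grade 3, is a Grade 3 or higher immune-related event outside the endocrine exemption, yet the action is *Continue*.
- *Permissive only:* Grade 3 colitis is *Withhold*, and other Grade 3 immune-related events may be withheld or discontinued. Mandatory permanent discontinuation comes only at recurrence or Grade 4. This leaves resumption open without directing it, and the general instruction on resuming names pembrolizumab only.
- *In agreement with 6.1.1.1:* pneumonitis, hepatic events, nephritis and myocarditis are all permanently discontinued at Grades 3 and 4.

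**Patients under both rules.** Planned Phase 1a enrolment before backfill (Synopsis) is 12 + 9 = 21 to 24 + 18 = 42. Up to 20 backfill patients bring the maximum to 42 + 20 = 62.

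**The case against.** The strongest reply is that the rules can be read together. Section 6.1.1.1 is mandatory and narrow: Phase 1a, 28 days, DLTs only. The tables also serve later Phase 1a cycles and Phase 1b (up to about 140 patients), so every row keeps a use outside the window, and the 6.6.1 introduction is permissive. Section 7.1 makes unacceptable toxicity a reason to stop, and a DLT fits that readily. The DLT-evaluable definitions in Protocol 9.3 and SAP Table JZMA.6.1 speak of DLT patients discontinuing treatment, which points the same way, although they use 3 weeks and 28 days respectively.

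There are also safeguards. The note closing 6.6.2 asks sites to consult the sponsor on any suspected immune-related event of Grade 2 or above, which would reach hypothyroidism. Sections 4.1 and 9.5 provide for joint sponsor and investigator review of safety data before escalation.

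Most of this stands, and it shows the likely intent. It does not remove the conflict. The rows themselves are directive, those for fatigue and febrile neutropenia are as specific by event and grade as the DLT criteria, and no line says which rule governs. The consultation note in 6.6.2 does not reach the non-immune events in 6.6.1.

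A reader might infer that the whole of 6.6.2 contradicts 6.1.1.1. It does not: one row conflicts directly, several are permissive and several agree. A reader might also infer that dose escalation is distorted. The documents do not support that. An event counts as a DLT whatever dosing follows, and Protocol 4.1.1 and SAP 5.1.3 keep a patient with a DLT-qualifying event evaluable even below 75% of doses. The SAP table's wording, read alone, would not fit a DLT patient who was held and reduced rather than discontinued, but those operative rules still count that patient.

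**Conclusion.** The point holds for the listed 6.6.1 rows and for Grade 4 or symptomatic Grade 3 hypothyroidism in 6.6.2. These are two stated rules with opposite instructions, not a missing detail, and they concern patient safety in a first-in-human study, so they should be reconciled.

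The size is modest. The documents give no DLT rate by event type, so the number affected cannot be estimated; I expect it to be small. The 21 to 42 is the number of patients to whom both rules apply, not the number at risk of conflicting instructions, which is limited to those with a DLT of an overlapping type. Nothing in the documents supports reading this as expected unnoticed re-dosing or as an error in the mTPI-2 DLT count. The conclusion assumes that 6.1.1.1 is meant to prevail; the hepatic overlap also assumes that the printed Grade 3 limits apply to 6.6.1.

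**What to change.** Add to both 6.6.1 and 6.6.2:

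> For a DLT as defined in Section 6.1.1.1 occurring in the DLT observation period in a Phase 1a dose-escalation (DLT-evaluation) patient, Section 6.1.1.1 applies and study treatment is discontinued; these tables apply to all other events, including DLT-equivalent toxicities.

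The sentence is limited to dose-escalation patients for a reason. Section 4.1.1 classes events in backfill patients that meet the DLT criteria within the DLT period as DLT-equivalent toxicities, not DLTs. A broader sentence would impose discontinuation on up to 20 backfill patients, which the documents do not clearly require. The sponsor should state explicitly whether backfill patients are also to be discontinued.

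The cost is one sentence in each of two sections and one decision on backfill, with no added patients, procedures or analyses. The small downside is that a DLT patient who might tolerate a lower dose comes off treatment, as 6.1.1.1 already requires.
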